5.2.1 PLD

Pegylated liposomal doxorubicin will be administered intravenously at a dose of 40 mg/m² on Day 1 of each 28-day cycle. Doses up to 90 mg must be diluted in 250 mL of 5% Dextrose Injection, USP for administration to the participant; doses exceeding 90 mg will be diluted in 500 mL of 5% Dextrose Injection, USP for administration to the participant. The initial infusion rate should be 1 mg/min to minimize the risk of infusion reactions. If no infusion-related adverse reactions are observed, the rate of infusion can be increased to complete administration of the drug over one hour in accordance with institutional guidelines.

The dose of PLD should be calculated at the beginning of each cycle.

5.2.2 PF-07901801

PF-07901801 will be administered by intravenous infusion on Day 1, Day 8, Day 15 and Day 22 of the 28-day Cycle 1 and on Day 1 and Day 15 of subsequent 28-day cycles (i.e., Cycle 2 onward) for dose levels 1 and 2. For dose level 3, PF-07901801 will be administered by intravenous infusion on Day 1 and 15 of a 28-day cycle starting from Cycle 1.

The dose of PF-07901801 will be based upon the dose level cohort to which the participant is assigned; the duration of infusion is dependent on dose level: dose levels less than or equal to 33 mg/kg infused over 60 min and doses greater than 33 mg/kg infused over 90 minutes and will have doses equal to or less than 2500 mg in 250 mL and doses 2501 mg or more in 500 mL or neat drug if the drug volume is over 500 mL. At the investigator's discretion, the duration of infusion can be lengthened but not abbreviated. Preparation instructions can be found in the IPM.

In any cycle in which PLD and PF-07901801 are administered on the same day, PLD treatment will precede administration of PF-07901801. A delay before initiation of PF-07901801 (TTI-622) is not mandated.

For the purposes of safety decisions that guide cohort expansion and considerations of PF-07901801 dose adjustment, the safety period will consist of the 28-day Cycle 1.

A participant who completes at least four cycles of PF-07901801 in combination with PLD and experiences PLD-mediated toxicity that requires its discontinuation may revert to PF-07901801 monotherapy with the next cycle provided the participant has not experienced

disease progression and PF-07901801 re-treatment guidelines as described in Section 9.1.2 are met

Preparation of the PF-07901801 dose is based on body weight in kg and should be calculated at the beginning of each cycle and may be used throughout the cycle unless a participant experiences a >10% variation in weight within a cycle.

As described previously and presented again in Table 12 below, three dose levels of PF-07901801 are planned to be evaluated in combination with fixed-dose PLD in a 3+3 study design in the dose escalation portion of the study. After review of emerging safety and other data from these dose levels, alternate PF-07901801 dose levels may be evaluated to more fully understand safety or pharmacodynamics of PF-07901801 in combination with PLD, to more fully identify dose-limiting toxicities, to more clearly define the maximum tolerated dose, and/or to optimize selection of the most appropriate dose(s) for evaluation in the expansion cohorts.

Table 12. PF-07901801 Dose Levels Planned for Evaluation in Combination with PLD

Dose Level	PF-07901801 Dose
1	12 mg/kg
2	24 mg/kg
3	48 mg/kg

If Dose Level 1, 12 mg/kg, is found to be intolerable, a lower dose level may be evaluated. If Dose Levels 2 or 3 are not tolerated, intermediate dose levels may be evaluated.

5.3 Criteria for Treatment Discontinuation

Participants may withdraw voluntarily from participation in the study or from study treatment at any time and for any reason. A participant 's participation in the study may terminate at his/her/their request or on the basis of the investigator's clinical judgment. The reason for participant withdrawal will be documented in the source data and noted on the electronic case report form (eCRF).

At a minimum, all participants who discontinue study treatment, including those who refuse to return for a final visit, will be contacted for safety evaluations at the 30-Day Safety Follow-Up Visit.

If such withdrawal occurs, or if the participant fails to return for visits, the investigator must determine the primary reason for a participant's withdrawal from the study and record the information on the eCRF. If the reason for withdrawal is an adverse event, monitoring should continue until the outcome is evident. The specific event or test result(s) must be recorded in the eCRF. At the discretion of the sponsor, participants may also be removed from the study.

It should be clearly documented in the source data whether participants withdrew consent for participation in the study, including study treatment and participation in the long-term follow-up phase or if participants withdrew from study treatment but will continue further participation in the long-term follow-up portion of the study.

Treatment may be continued until one of the following criteria applies:

- An unacceptable adverse event or safety observation, such as a persistent moderate toxicity that is intolerable to the participant, that is in the opinion of the investigator clearly attributed to PF-07901801.
- An unacceptable adverse event or safety observation, such as a persistent moderate toxicity that is intolerable to the participant, that is in the opinion of the investigator clearly attributed to PLD and the participant has received fewer than four cycles of PLD. A participant who has completed four cycles of PLD treatment and experiences an adverse event that requires discontinuation of PLD may continue on study receiving PF-07901801 monotherapy after discussion with the sponsor medical monitor.
- Any event which would cause PF-07901801 or PLD to be modified by more than two
 dose reductions or to be held for more than 42 days from the last administered dose and
 is not attributable to a particular agent of the combination regimen; exception is made
 for participants who are receiving meaningful disease control and the investigator feels,
 with sponsor medical monitor concurrence, that continued treatment is in the best
 interest of the participant.
- Any treatment-related adverse event that is deemed life-threatening, regardless of grade. For Grade 4 adverse events, discontinuation of PF-07901801 should be considered. If it is in the participant's best interest to continue PF-07901801 per investigator assessment, withhold dose until resolved to ≤Grade 1 or baseline, then reduce by 1 dose level. If the participant is receiving disease control and the investigator judges that continued treatment may be in the participants best interest, PF-07901801 treatment may be resumed when the adverse event resolves to a level that meets re-treatment criteria. In consultation with the sponsor medical monitor, the dose level may be resumed; exception is made for participants in whom the life-threatening adverse event is attributed to PLD and the participant has received at least four cycles of PLD treatment and the investigator feels, with sponsor medical monitor concurrence, that continuation with PF-07901801 monotherapy would be reasonable.
- Documentation of objective (radiographic) disease progression; for participants with asymptomatic progression and in the absence of unacceptable toxicity, the participant should continue treatment and a confirmation scan should be conducted at least four weeks later to document objective progression prior to removing participant from study treatment. A participant should not be removed from study on the basis of change in CA-125 level in the absence of objective or asymptomatic progression.
 - The mechanism of immunotherapy is mechanistically distinct from other types of therapy. The patterns of response and progression to immunotherapeutic agents, such as TTI-622, often differ temporally, qualitatively and quantitatively from those observed with cytotoxic and targeted agents. The goal of immunotherapy is to overcome immunosuppression induced by a tumor and its microenvironment, thereby allowing the immune system to develop or activate an immune response that

[figure not shown]
targets and kills cancer cells. Some patients have experienced pseudo-progression or immune-mediated inflammation, in which areas of disease showed an initial surge followed by shrinkage that led to development of immune-related disease response criteria that supports continued treatment beyond progression in patients whose clinical conditions have not worsened and who have not experienced severe toxicities. Recognizing that immunotherapy represents a paradigm shift in oncology treatment, patients with an early observation of disease progression but without deterioration in clinical conditions or unacceptable toxicity and who consent should continue treatment until disease progression is verified by a repeated disease assessment at least four weeks later.

- Unacceptable toxicity which in the opinion of the investigator cannot be attributed to a specific study agent.
- An intercurrent illness or change in the participant's condition that renders the participant unsuitable for further treatment in the opinion of the investigator; exception may be made for participants in whom the intercurrent illness or change in condition is thought to render the participant ineligible for continued treatment with PLD and the participant has received at least four cycles of PLD and the investigator feels, with medical monitor concurrence, that continuation with PF-07901801 monotherapy would be reasonable and the participant meets criteria for PF-07901801 re-treatment
- Significant noncompliance with study protocol.
- Withdrawal of consent for participation in the treatment portion of the study (participant may participate in Long-Term Follow-Up assessment of survival and disease status [if withdrawn prior to documentation of objective disease progression] if consent for Long-Term Follow-Up assessment is not withdrawn).
- Participant is lost to follow-up.
- Termination of the study by the sponsor.

At the investigator's discretion and in agreement with the sponsor, treatment after objective disease progression may continue for a participant who is clinically stable and receiving meaningful disease control and the investigator feels it is in the participant's best interest to continue treatment. The reason for continuing treatment must be thoroughly discussed, agreed with the sponsor medical monitor, and clearly documented in the study files.

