Dose reductions may be warranted if worsening of symptoms or laboratory values is clinically significant in the opinion of the investigator and in the case of unacceptable treatment-related adverse events. Recognizing that it may be difficult to make attribution to one agent or the other in the combination regimen and in collaboration with the medical monitor, best efforts should be made to consider the underlying reason for the worsening of symptoms or development of a treatment-related adverse event so that dosing of the appropriate study drug can be modified.

Except in the case of proteinuria, asymptomatic laboratory abnormalities should not result in dose interruptions, modifications, or discontinuation of study therapy unless determined by the investigator to be clinically significant or life-threatening.

The investigator should withdraw a participant from all studyrelated treatment for any of the following reasons:

- An unacceptable adverse event or safety observation, such as a persistent moderate toxicity that is intolerable to the participant, that is in the opinion of the investigator clearly attributed to PF-07901801
- An unacceptable adverse event or safety observation, such as a persistent moderate toxicity that is intolerable to the participant, that is in the opinion of the investigator clearly attributed to PLD and the participant has received fewer than four cycles of PLD. A participant who has completed four cycles of PLD treatment and experiences an adverse event that requires discontinuation of PLD may continue on study receiving PF-07901801 monotherapy.
- Any event which would cause PF-07901801 or PLD to be modified by more than two dose reductions or to be held for more than 42 days from the last administered dose and is not attributable to a particular agent of the combination regimen; exception is made for participants who are receiving meaningful disease control and the investigator feels, with medical monitor concurrence, that continued treatment is in the best interest of the participant
- Any treatment-related adverse event that is deemed life-threatening, regardless of grade; exception is made for participants in whom the life-threatening adverse event is attributed to PLD and the participant has received at least four cycles of PLD treatment and the investigator feels,

- with medical monitor concurrence, that continuation with PF-07901801 monotherapy would be reasonable.

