3.5.2.1.5 Dose-Limiting Toxicity

The dose level of 8.0 mg/kg was associated with a reversible dose-limiting toxicity of Grade 4 platelet count decreased in one participant, which was asymptomatic, reversible and managed without any clinical sequelae. This cohort was expanded and no other participant experienced this or any other dose-limiting toxicity.

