9.1.1 PF-07901801 Treatment Interruptions

Treatment with PF-07901801 may be interrupted for up to 56 days for toxicity assessed as related to treatment with PF-07901801; treatment may be interrupted for up to 28 days for reasons unrelated to toxicity if the participant is receiving disease control and after discussion with the sponsor medical monitor. Treatment may be re-instated after discussion with the medical monitor. In general, if an interruption of more than 56 days is required due to adverse events, PF-07901801 will be permanently discontinued; however, if in the judgment of the investigator, the participant is likely to derive disease control from PF-07901801 after a hold of more than 56 days, study drug may be re-started with the approval of the sponsor medical monitor. The infusion duration may be increased and/or other precautionary measures instituted after discussion with the sponsor medical monitor, but the PF-07901801 dose level does not require modification when administration is re-started. Longer interruptions may be acceptable on a participant -by- participant basis at the discretion of the investigator after discussion with the sponsor medical monitor.

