9.1.5 Non-Hematologic Adverse Events Related to PF-07901801 Administration

PF-07901801 (TTI-622) dose adjustments based on the occurrence of non-hematologic treatment-related adverse events are described in Table 17.

Table 17. Management of Non-Hematologic Adverse Events Associated with PF-07901801 Administration

Observation	Management Guidelines
Grade ≥3 events with the following exceptions: • Nausea and/or vomiting lasting <72 hours with supportive care	 For Grade 3 events, delay PF-07901801 dosing until the re-treatment criteria are met, then resume PF-07901801 at one dose level reduction No dose reduction is required for the exceptions listed
 Fatigue lasting ≤72 hours Laboratory abnormalities lasting <72 hours and judged by the investigator as not clinically significant 	• For Grade 4 events, discontinuation of PF-07901801 should be considered unless the adverse event was transient and/or asymptomatic and/or not clinically significant. If the investigator judges that continued treatment may be in the participant 's best interest, PF-07901801 treatment can be resumed when the adverse event resolves to a level that meets re-treatment criteria. In consultation with the medical monitor, the dose level may be reduced.

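### The Synopsis and Section 5.3 differ on a Grade 4 event deemed life-threatening, and two hold limits for unattributable toxicity have no precedence rule

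*Protocol*

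**What the plan says.** **Life-threatening events.** The Synopsis introduces its list with "The investigator should withdraw a participant from all studyrelated treatment for any of the following reasons". One reason listed is any treatment-related event "deemed life-threatening, regardless of grade; exception is made for participants in whom the life-threatening adverse event is attributed to PLD", provided at least four PLD cycles have been given and the medical monitor agrees to PF-07901801 monotherapy. No other exception is given.

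Protocol Section 5.3 repeats the criterion, for events "deemed life-threatening, regardless of grade. For Grade 4 adverse events, discontinuation of PF-07901801 should be considered", and adds two restart sentences. In the first, if continuing is in the participant's interest, sites "withhold dose until resolved to ≤Grade 1 or baseline, then reduce by 1 dose level". In the second, a participant with disease control may restart once re-treatment criteria are met, and "In consultation with the sponsor medical monitor, the dose level may be resumed". The parallel Grade 4 row of Table 17 (Section 9.1.5) ends differently: "In consultation with the medical monitor, the dose level may be reduced". Section 9.1.1, on interruptions generally, says the "dose level does not require modification when administration is re-started".

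**Hold limits for unattributable toxicity.** The Synopsis and Section 5.3 stop treatment when a drug would be held more than 42 days from the last administered dose. They except participants with meaningful disease control, with medical monitor concurrence. Table 27 (Section 9.3) covers unattributable events of Grade 3 or higher, with listed exclusions. If there is no recovery after a delay of more than 21 days, PF-07901801 is discontinued and the participant is removed from the study. Table 27 states no exception and does not say when the delay starts.

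**The concern.** Whether to re-expose a patient after a life-threatening reaction, and at what dose, is a safety decision. It should not depend on which section of the protocol a site opens. The Synopsis points to withdrawal. Section 5.3, under the same criterion, makes stopping a matter for consideration and then describes restart. If treatment does restart, Section 5.3 both requires a reduction and appears to permit the previous dose.

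The hold limits raise a smaller version of the same problem. A participant with an unresolved, unattributable Grade 3 event could have passed the Table 27 limit while still inside the Section 5.3 limit. If she has disease control, Section 5.3 sets no fixed ceiling at all.

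**Working it through.** The plan gives no figure to reproduce. Part 1 is a comparison of texts; part 2 needs only subtraction.

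**Part 1. Instructions side by side**

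| Place | Event | Instruction | Restart of PF-07901801 |
|---|---|---|---|
| Synopsis | Related, deemed life-threatening, any grade | Should withdraw from all study treatment | Monotherapy only: PLD-attributed event, at least four PLD cycles, monitor concurrence |
| Section 5.3, same bullet | Same criterion, then Grade 4 | Consider stopping PF-07901801 | (a) Grade 1 or less or baseline, one level lower; or (b) disease control, re-treatment criteria met, dose resumed |
| Table 17, Grade 4 row | Non-hematologic | Consider stopping unless transient, asymptomatic or not clinically significant | Re-treatment criteria met; dose may be reduced |
| Table 20, Grade 4 row | Infusion reaction | Stop the infusion | Barred if PF-07901801 is judged the cause and stronger prophylaxis is thought insufficient |

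1. *Is every Grade 4 event life-threatening?* No. Section 3.5.2.1.5 reports a "Grade 4 platelet count decreased in one participant, which was asymptomatic, reversible and managed without any clinical sequelae". Section 13.1.2 defines immediately life-threatening as being at risk of death at the time of the event, which is separate from grade.
2. *Can an event be both?* Yes. Table 19 defines a Grade 4 infusion reaction by life-threatening consequences. Section 13.4 does the same for terms not listed in CTCAE, and SAP Section 8.4 labels Grade 4 that way.
3. *Test case.* Take a Grade 4 infusion reaction related to PF-07901801. The Synopsis says withdraw. Section 5.3 says consider stopping, with restart possible. Table 20 bars re-infusion only if both of its conditions hold. These are three different instructions for one event.
4. *Restart dose.* The adverse-event line of Table 14 (re-treatment criteria) is Grade below 2 or baseline, so routes (a) and (b) have nearly the same recovery threshold. The real difference is the dose. Route (a) follows the Grade 4 anemia row of Table 16. Route (b) follows the Table 17 row, with 'resumed' where that row has 'reduced', so a slip is likely.

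**Part 2. The two hold limits on one scale**

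Days since last dose = dosing interval + days past the due dose.

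*Assumption A:* the Table 27 delay starts at the first missed scheduled dose, and the 42 days run from the held drug's own last dose.

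| Drug and interval | Table 27 limit, days since last dose | Section 5.3 limit | Reached first |
|---|---|---|---|
| PF-07901801 weekly (Cycle 1, dose levels 1 and 2) | 7 + 21 = 28 | 42 | Table 27, by 14 days |
| PF-07901801 every 14 days | 14 + 21 = 35 | 42 | Table 27, by 7 days |
| PLD every 28 days | 28 + 21 = 49 | 42 | Section 5.3, by 7 days |

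*Assumption B:* the Table 27 delay starts at the last dose. The comparison is then 21 against 42 for either drug, and Table 27 is reached 21 days earlier.

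The PLD row holds only with a separate clock for each drug. Table 27 delays study treatment as a whole, and Section 5.3 counts from the last administered dose. If that means the last dose of either drug, with PF-07901801 on schedule and the delay counted from its due dose, Table 27 is reached at 28 or 35 days, before 42.

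Example under A, 14-day dosing: 36 days after the last dose the delay is 36 − 14 = 22 days. That is over 21, so Table 27 stops; 36 is below 42, so Section 5.3 does not.

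**The case against.** The best defence is that the Grade 4 sentences in Section 5.3 concern only Grade 4 events not deemed life-threatening. The bullet sits under a lead-in that treatment continues until a listed criterion applies. It keeps the life-threatening criterion intact, and it keeps the PLD exception, which has little purpose unless stopping remains the rule. This reading is plausible and may be what was meant. But Section 5.3 does not say it and places the text inside the life-threatening bullet, and Table 20 can still allow re-infusion after an event that Table 19 calls life-threatening.

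On dose, the two sentences can be read as a default and an exception, and the permissive sentence in Section 9.1.1 is general and need not override event-specific rows. Both points stand, so the dose issue is one of unclear wording.

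On hold limits, several stopping rules are ordinarily all met by obeying the earliest. Table 27 has a narrower trigger than Section 5.3, is titled as general guidelines, and comes with advice to discuss cases with the medical monitor. Section 5.3 also has a separate stop for unacceptable unattributable toxicity. This reduces the second point to a missing statement of precedence and scope.

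**Conclusion.** The point holds in a limited form. Events that are both Grade 4 and deemed life-threatening receive different instructions in the Synopsis and Section 5.3; for infusion reactions, Table 20 differs again. Section 5.3 is also unclear on the restart dose. For unattributable Grade 3 or higher toxicity, Table 27 stops PF-07901801 7, 14 or 21 days before Section 5.3, depending on the dosing interval and on an assumed start for the Table 27 clock. No text says which limit governs or whether the disease-control exception reaches Table 27.

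A reader might infer more than the documents support:

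- *Withdrawal is mandatory in the Synopsis.* The verb there is 'should', and there is a PLD exception.
- *Every Grade 4 event is in conflict.* The asymptomatic platelet case shows otherwise.
- *The two hold limits cannot both be obeyed.* Stopping at the earlier one obeys both.
- *Section 5.3 is the stricter rule for PLD.* That depends on a separate clock for each drug, which the protocol does not state.
- *The trial's statistical results are affected.* Nothing here touches the DLT definition, the response rule or the sample size.

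This is contradictory safety wording that should be corrected at the next amendment.

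**What to change.** **1. Life-threatening events.**

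- Use one identical bullet in the Synopsis and Section 5.3: a related event deemed life-threatening, whatever its grade, leads to withdrawal from all study treatment, with the existing PLD exception kept.
- State that the Grade 4 restart text applies only to Grade 4 events not deemed life-threatening. The restart dose is set by the applicable row of Tables 16 to 18 and, where no row applies, is one dose level lower.
- Delete the sentence allowing the dose level to be resumed, and note in Section 9.1.1 that its no-modification sentence does not override these rules.
- Align the Grade 4 row of Table 20 with the bullet.
- If the sponsor does intend restart after life-threatening events, put that same text in the Synopsis.

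**2. Unattributable events.**

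- State that the earlier of the Table 27 and Section 5.3 limits governs.
- Define when the Table 27 delay starts, and say whether the disease-control exception applies to it.
- In both places in Table 27, replace removal from the study with discontinuation of study treatment. Section 5.1 requires survival follow-up for all participants, and overall survival is a secondary endpoint.
- The 56-day limits in Sections 9.1.1 and 9.2.1 can stay as they are.

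The cost is amendment wording in the Synopsis, Section 5.3, Section 9.1.1 and Tables 20 and 27. Sample size, visits and procedures do not change.
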